### **1.3. Team involved in the study**

Two separate teams will be involved in this study:

- An independent statistical centre (ISC) composed of an unblinded statistician and programmers. They will be in charge of preparing outputs for the interim analyses. These individuals will work out of an office that is in a separate geographic location to the sponsor and blinded team.
- A blinded team composed of a blinded statistician and programmers. They will be responsible of preparing the outputs for the end of study analysis.

For further details, the charter describes the operation of the interim reviews, as managed by the Data Review Committee (DRC).

## **2. STUDY DESIGN**

### **2.1. Synopsis of Study Design**

This is a multi-centre, multi-country, double-blind, randomised, placebo-controlled Phase 2b study. The study will have a single-blind placebo run-in period and will be adaptive with respect to the number of subjects recruited into each dose group.

Four doses of NT-814 (40 mg once a day, 80 mg once a day, 120 mg once a day and 160 mg once a day) will be investigated and compared to placebo, in five parallel groups. All subjects will receive placebo for the last 2 weeks of the screening/baseline period, after which subjects who meet all of the eligibility criteria will be randomised into the study. Subjects will initially be randomised 1:1:1:1:1 to each of the treatment groups, with the randomisation ratio subject to change in response to emerging efficacy and safety data. Regardless of any changes to the randomisation ratio, subjects will continue to receive the dose regimen they were randomised to for the full 12-week treatment period.

Subjects will participate in the study for a total of approximately 19 weeks, comprising a screening & baseline period (3 weeks), 12 weeks of double-blind treatment and then a final follow up visit, 4 weeks after the end of the treatment period. There will be a total of 8 visits whilst participating in the study.

### **2.2. Randomization Methodology**

Eligible subjects will be randomised on Day 1 to NT-814 or placebo. Randomisation will be performed centrally via an interactive web response system (IWRS) and is integrated into the Electronic Data Capture (EDC) system. The randomisation schedule (both the initial and any updates following IA) will be produced and entered into the IWRS by Pharm Olam International according to their Standard Operating Procedures.

An adaptive design will be used to maximise the efficiency of the study through discontinuation or reduction in the number of subjects randomised to doses that are found, on the basis of emerging data, to be either insufficiently effective or no more effective than an adjacent lower dose. Doses may also be discontinued for safety reasons and the randomisation ratio may be adjusted in favour of one or more doses without necessarily discontinuing other doses.

On successful completion of screening and confirmation of eligibility, subjects will initially be randomised in a 1:1:1:1:1 ratio to receive either NT-814 40 mg/day, 80 mg/day, 120 mg/day, 160 mg/day or placebo. Randomisation will be stratified by region (North America or Europe). After completion of the first interim review the randomisation ratio may be changed. Regardless of any changes to the randomisation ratio, subjects will continue to receive the dose regimen they were randomised to for the full 12-week treatment period.

The initial estimated sample size for the study is 165 subjects. However, the total number of subjects may be higher or lower according to the outcome of the interim analyses.

### **2.3. Stopping Rules and Unblinding**

Patients can decide at any time to withdraw consent from the study. Investigators can decide at any time during the study to discontinue treatment for an individual patient based on their own medical judgment. Reasons for discontinuing a subject should be documented in the CRF, and patients will be encouraged to participate to the final follow-up/early termination visit even if they discontinue study medication.

The Sponsor may terminate the study for safety or administrative reasons at any time. The Data Review Committee (DRC) is responsible for overseeing the safety of the study and the DRC Charter includes specific criteria for stopping or suspending the study.

Study investigators (principal and sub) will be given access to the IWRS system for the purposes of emergency unblinding. Investigators are permitted to unblind treatment for a subject if it is deemed that knowledge of the subject's treatment will impact subject's future medical care. If a suspected unexpected serious adverse reaction (SUSAR) occurs that requires expedited reporting to the relevant regulatory agency/Institutional Review Board (IRB) /Independent Ethics Committee (IEC), then the blind will be broken for the relevant subject by Emas safety group through IWRS, in order to provide the regulatory agencies with the knowledge of the event and the causal agent. A blinded (or an unblinded report if required) copy of the report will be provided to the investigators and the relevant IRB/IEC. The study operational team will remain blinded to treatment allocation until the database has been locked at the end of the study.

If unblinding occurs accidentally this will be considered a protocol deviation which must be documented in the subject's medical notes and in the trial master file (TMF), and the Sponsor must be informed.

#### **2.4. Study Procedures**

The schedule of assessments, as outlined in the study protocol, is provided in

Table 1.

**Table 1 Schedule of Assessments**

Procedure	Screening Visit 1 (Visit 1)	Screening Visit 2 (Visit 2)	Baseline (Visit 3)	Week 2 (Visit 4)	Week 4 (Visit 5)	Week 8 (Visit 6)	Week 12 (Visit 7)	Week 16 Follow-up/Early Termination visit b (Visit 8)
Visit Day	-21 a	-14	1	15	29	57	85	113
Allowable window	a	±2 days	0	±3 days	±3 days	±4 days	±4 days	±5 days
Informed Consent c	X							
Medical History/Concomitant Diseases	X	X						
Demography	X							
Physical Exam		X	X d					X d
Inclusion/Exclusion Criteria	X	X e	X f					
Review of Concomitant Medications	X							X
Vital Signs g		X	X	X	X	X	X	X
12-lead ECG		X	X	X	X	X	X	X
AE and SAE Recording		X						X
Issue Paper Diary / Training	X							
Paper Diary Completion (once daily)	X-----X h							
Issue eDiary / Training / Compliance check		X	X	X	X	X	X	
eDiary Completion (twice daily)		X						X i
Study Drug Dispensing/Training		X	X		X	X		
Placebo Treatment		X-----X j						
Study Drug Collection/Compliance			X	X	X	X	X	
Randomisation			X					
Daily Dosing (evening before bedtime)			X				X	
MenQoL-I			X		X	X	X	X
HFRDIS			X	X	X	X	X	X
Pittsburgh Sleep Quality Index			X		X	X	X	X
Insomnia Severity Index			X		X	X	X	X
Columbia Suicide Severity Rating Scale			X		X		X	X
Beck Depression Inventory II			X	X	X	X	X	X
Clinical Chemistry and Haematology		X	X	X	X	X k	X	X
Blood sample for NT-814 concentration				X	X	X	X	
Blood sample for bone turnover markers			X				X	X
Urine pregnancy Test		X						
Urinalysis		X	X	X	X		X	X

- a Screening visit 1 must be at least 6 days before Screening Visit 2 to allow at least 6 days of paper diary data to be completed. It can be earlier than Day -21 if needed to enable prohibited concomitant medications to be washed-out.
- b An Early Withdrawal/Safety Follow-up visit will be performed if the subject withdraws after the Baseline visit. This visit will consist of the same assessments as the Week 16 Follow-up visit and should be scheduled within 14 days of the early termination date or discontinuation of investigational product.
- c Informed consent will be obtained prior to any screening procedures being performed. Consent can be obtained prior to Screening Visit 1 or at the actual visit.
- d Symptom directed examination, if required.
- e The paper diary Hot Flush requirements, as well as the other inclusion/exclusion criteria, will be assessed at Screening Visit 2.
- f The eDiary Hot Flush requirements will be assessed and other inclusion/exclusion criteria will be reviewed at the Baseline visit.
- g Systolic and diastolic blood pressure, pulse rate, temperature and weight will be recorded at all visits except Screening Visit 1. Waist circumference will be recorded at all visits except Screening Visits 1 and 2. Height will be measured at Screening Visit 2 only.
- h Subjects will complete a paper diary once a day for 7 days in between Screening Visit 1 and Screening Visit 2 (a minimum of 6 days of diary data is required to confirm eligibility).
- i Subjects will complete the eDiary twice a day, from the evening of Screening Visit 2 until they exit the study.
- j At Screening Visit 2, subjects will commence placebo treatment (the placebo run-in period). Their first dose of placebo will be taken in the clinic and all subsequent doses at home once a day in the evening (starting the following day) up until the day before the Baseline visit.
- k At Week 8, this blood sample is for clinical chemistry only.

## **2.5. Efficacy, Pharmacokinetic, and Safety Variables**

### 2.5.1. Efficacy Variables

#### 2.5.1.1. Primary Efficacy Variables

There are four co-primary efficacy endpoints:

- Mean change from baseline in mean daily frequency of moderate and severe hot flushes (HF) from baseline to Week 4
- Mean change from baseline in mean daily frequency of moderate and severe HF from baseline to Week 12
- Mean change from baseline in mean severity of moderate and severe HF from baseline to Week 4
- Mean change from baseline in mean severity of moderate and severe HF from baseline to Week 12

#### 2.5.1.2. Secondary Efficacy Variables

The secondary efficacy endpoints include:

- Mean change from baseline in frequency of mean daily moderate and severe HF from baseline to Weeks 1, 2, 8 and 16
- Mean change from baseline in mean severity of moderate and severe HF from baseline to Weeks 1, 2, 8 and 16
- Mean change from baseline in mean daily frequency of all HF from baseline to Weeks 1, 2, 4, 8, 12 and 16
- Mean change from baseline in mean severity of all HF from baseline to Weeks 1, 2, 4, 8, 12 and 16
- Mean change from baseline in the mean daily HF Score (frequency x severity) at Weeks 1, 2, 4, 8, 12 and 16
- Responder analyses: proportion of subjects with >50% and >80% reduction from baseline in mean daily HF frequency at Week 12
- Mean change from baseline in mean daily number of night-time awakenings (NTA) secondary to HF at Weeks 1, 2, 4, 8, 12 and 16
- Mean change from baseline in mean daily number of all NTA at Weeks 1, 2, 4, 8, 12 and 16
- Change from baseline in the Global and individual domain scores of the Pittsburgh Sleep Quality Index at Weeks 4, 8, 12 and 16
- Change from baseline in the Insomnia Severity Index score at Weeks 4, 8, 12 and 16
- Change from baseline in the HFRDIS scores at Weeks 2, 4, 8, 12 and 16
- Change from baseline in the MenQoL-I scores at Weeks 4, 8, 12 and 16
- Change from baseline in the Beck Depression Inventory II scores at Weeks 2, 4, 8, 12 and 16

### 2.5.2. Pharmacokinetic Variables

Exposure-response modelling will be undertaken on a number of efficacy and safety endpoints on an exploratory basis. These analyses will be described in a separate Exposure-Response Data Analysis Plan and the resulting data will be reported in a report separate from the CSR.

### 2.5.3. Safety Variables

Safety assessments performed during the study included physical examinations, measurement of vital signs, 12-lead electrocardiograms (ECGs), clinical laboratory evaluations including hematology, serum chemistry, and urinalysis, and monitoring of adverse events.

The safety endpoints include:

- Change from baseline in clinical laboratory assessments:
  - ✓ At Weeks 2, 4, 12 and 16 for haematology and urinalysis
  - ✓ At Weeks 2, 4, 8, 12 and 16 for clinical chemistry
- Change from baseline in vital signs (blood pressure, pulse rate, temperature) at Weeks 2, 4, 8, 12 and 16
- Change from baseline in weight, waist circumference and body mass index at Weeks 2, 4, 8, 12 and 16
- Proportion of subjects with clinically significant abnormal ECG findings at each visit
- Proportion of subjects with non-significant abnormal ECG findings at each visit
- Change from baseline at Weeks 2, 4, 8, 12 and 16 in ECG intervals (RR, PR, QT, QTc and QTcF)
- Proportion of subjects with absolute QTcF values by category at each visit: <450, >450 to <480, >480 to <500, >500 msec
- Proportion of subjects with change from baseline in ECG QTcF values by category at Weeks 2, 4, 8, 12 and 16: <0, >0 to <30, >30 to <60, >60 msec
- Change from baseline in the electronic Columbia Suicide Severity Rating Scale (eC-SSRS) at Weeks 4, 12 and 16
- Change from baseline to Weeks 12 and 16 in:
  - Serum concentration of bone-specific alkaline phosphatase (BALP)
  - Serum concentration of procollagen type 1 N-terminal propeptide (PINP)
- Nature and severity of AEs
- Withdrawals due to an AE
- Use of concomitant medications

### 3. SUBJECT POPULATIONS

#### 3.1. Population Definitions

The following subject populations will be evaluated and used for presentation and analysis of the data:

**Screen Analysis Set:** the screened population will include all subjects with informed consent.

**Randomized Analysis Set:** the randomized population will include all subjects with a randomization date and number.

**Safety Analysis Set:** All subjects who receive at least one dose of double-blind study drug irrespective of treatment received. Subjects will be analysed according to treatment received.

**Full Analysis Set (FAS):** All randomised subjects who received at least one dose of double-blind study drug, irrespective of treatment received, and have hot flush data for at least 7 days' worth of post-treatment assessments (i.e. requirement for the primary efficacy endpoint). Subjects will be analysed according to randomised treatment. This is the primary efficacy analysis set for the study.

**Modified Full Analysis Set (mFAS):** All subjects in the FAS excluding those who took non-hormonal treatments (anti-depressants, alpha-2 agonists, gabapentinoids and cannabis) or over the counter herbal treatments (intended to treat menopausal symptoms) that may have had a confounding effect on hot flash frequency and/or severity at any time during the study (defined as within 28 days before the start of Screening Visit 2 through to the Week 12 visit, inclusive). The medications entered in EDC have been reviewed by Sponsor's blinded Medical Expert, and the following final list of PREFERRED NAME was confirmed:

CLONIDINE  
CLONIDINE HYDROCHLORIDE  
CIMICIFUGA RACEMOSA  
TRIFOLIUM PRATENSE  
CIMICIFUGA RACEMOSA;HYPERICUM PERFORATUM  
CANNABIS SATIVA  
GABAPENTIN  
PREGABALIN  
AMITRIPTYLINE  
NORTRIPTYLINE  
CITALOPRAM  
CITALOPRAM HYDROBROMIDE  
ESCITALOPRAM  
ESCITALOPRAM OXALATE  
FLUOXETINE  
FLUOXETINE HYDROCHLORIDE  
PAROXETINE  
PAROXETINE HYDROCHLORIDE  
SERTRALINE  
SERTRALINE HYDROCHLORIDE  
BUPROPION  
BUPROPION HYDROCHLORIDE  
DESVENLAFAXINE  
DESVENLAFAXINE SUCCINATE

DULOXETINE  
DULOXETINE HYDROCHLORIDE  
VENLAXAFINE  
VENLAFAXINE HYDROCHLORIDE  
MIRTAZAPINE  
TRAZODONE  
TRAZODONE HYDROCHLORIDE  
VORTIOXETINE HYDROBROMIDE  
CALCIUM;CIMICIFUGA RACEMOSA EXTRACT;GENISTEIN;HERBAL EXTRACT  
NOS;MAGNESIUM;PIPER METHYSTICUM RHIZOME

.. Subjects will be analysed according to randomised treatment. This is the sensitivity efficacy analysis set for the study planned only if more than 20% of subjects are excluded from the FAS.

**Per Protocol (PP) Set:** All subjects in the FAS who completed the 12 week treatment period excluding those identified as having relevant protocol deviations (see Section 3.2). The list of relevant protocol deviations leading to exclusion from the PP population has been finalized during the blinded data review prior to database lock and unblinding of treatment allocation. Subjects will be analysed according to randomised treatment. This is the secondary efficacy analysis set for the study.

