### 11.3 Analysis Sets

The following data sets will be used for the statistical analysis.

1. **Safety Analysis Set:** All subjects who receive at least one dose of double-blind study drug irrespective of treatment received. Subjects will be analyzed according to treatment received
2. **Full Analysis Set (FAS):** All randomised subjects who received at least one dose of double-blind study drug, irrespective of treatment received, and have hot flush data for at least 7 days' worth of post-treatment assessments (i.e. requirement for the primary efficacy endpoint). Subjects will be analyzed according to randomised treatment. This is the primary efficacy analysis set for the study.
3. **Per Protocol (PP) Set:** All subjects in the FAS excluding those identified as having relevant protocol deviations.
4. **Exposure-Response (ER) Set:** all subjects who received at least one dose of double-blind study drug and for whom the PK data are considered sufficient.

Analysis Sets will be identified prior to the unblinding of the study data.

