### **11.9.1 Primary Efficacy Analysis**

The co-primary endpoints are the change from baseline in the mean daily frequencies of moderate and severe hot flushes in the 7 days before the week 4 and Week 12 visits, and the mean severity of moderate and severe hot flushes in the 7 days before the week 4 and Week 12 visits. The baseline assessment will be the last 7 days of the baseline diary completion period. Absolute and

---

changes from baseline in the mean daily frequencies and average hot flush severity will be summarised by treatment group. The change from baseline endpoint will be analysed using a mixed model repeated measures analysis. Pairwise statistical comparisons are planned for each NT-814 dose group (40 mg, 80 mg, 120 mg and 160 mg) versus placebo, presenting the adjusted mean treatment difference with its corresponding 95% confidence interval. In addition, treatment mean comparisons to placebo may be made via estimated means from a 4-parameter Emax model fit and trend test for increasing response with increasing dose based on isotonic regression modelling [details will be in the Statistical Analysis Plan].

The primary objective will be assessed by testing the following hypotheses for each NT-814 group versus placebo separately:

Null hypothesis ( $H_0$ ): There is no difference in the mean change from baseline in hot flush frequency [or severity] at Week 12 [or Week 4] compared to Baseline for the NT-814 treatment group compared to placebo.

$$H_0: \mu (\text{active}) = \mu (\text{placebo})$$

Alternative hypothesis ( $H_1$ ): There is a difference in the mean change from baseline in hot flush frequency [or severity] at Week 12 [or Week 4] compared to Baseline for the NT-814 treatment group compared to placebo.

$$H_1: \mu (\text{active}) \neq \mu (\text{placebo})$$

Absolute and changes from baseline in the in the mean frequency and severity will be summarised by treatment group.

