#### 4.3.2. Efficacy analysis

At each interim review, summaries by dose group will be provided on the FAS for each of the following:

- Mean daily frequency of moderate and severe HF at baseline, mean daily frequency of moderate and severe HF at each study week, including Week 4 and mean change and percent change from baseline in the mean daily frequency of moderate and severe HF at each study week.
- Mean severity of moderate and severe HF at baseline, mean severity of moderate and severe HF at each study week, including Week 4, and mean change from baseline in the severity of moderate and severe HF at each study week.

If available, summaries of the same data at later time-points (Week 8 and Week 12) will also be reviewed.

Mean daily frequency at each study visit will be calculated using the same method as the one described in section 4.2.11 based on the last 7 days with at least one available data in the evening and/or morning before the corresponding visit.

Mean weekly severity at each study visit will be calculated using the following:

$$\frac{[(\text{number of mild hot flushes for 7 days}) \times 1 + (\text{number of moderate hot flushes for 7 days}) \times 2 + (\text{number of severe hot flushes for 7 days}) \times 3]}{\text{total number of mild, moderate and severe hot flushes over 7 days}}$$

If the number of hot flushes is equal to 0, then the mean severity will be set to 0.

These 7 last days with available data should be within the 14 days prior to the CRF study visit, so in the following window: [CRF Visit date – 14; CRF Visit date], with at least one day within

the last 7 days prior to the study visit. In case of withdrawal, the day this ET visit happened will be checked to see in which windows it is and then to assign the corresponding timepoint. If a CRF visit has already been done at that timepoint, then the CRF visit date will be used. If less than 7 days fulfil these rules, only the correct data will be used in the derivation, and formula will be adjusted using the right number of days as denominator. Morning diary data on the day of a Visit will be included in the derivation as the morning diary is actually associated with the previous calendar day (a complete day is an evening then a morning diary).

In addition, emerging data will be evaluated via the two adaptive following algorithms to evaluate the emerging data at Week 4:

- (i) a Bayesian adaptive Emax (S-shaped) dose-response model fit, and

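### The primary efficacy set excludes dosed subjects with fewer than 7 diary days in total as an endpoint requirement, though the SAP's own derivation accepts fewer days

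*SAP*

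**What the plan says.** SAP 3.1 limits the FAS to randomised and dosed subjects who "have hot flush data for at least 7 days' worth of post-treatment assessments", explained in parentheses as "i.e. requirement for the primary efficacy endpoint". Protocol 11.3 sets the same condition and says of the FAS: "This is the primary efficacy analysis set for the study". The seven days are counted over the whole post-treatment period and are not tied to a visit.

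Protocol 11.9.1 defines the co-primary endpoints on "moderate and severe hot flushes in the 7 days before the week 4 and Week 12 visits" and gives no rule for shorter data.

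SAP 4.3.2 does give one. Qualifying days must lie in the 14 days before the visit, "with at least one day within" the final seven. It continues: "If less than 7 days fulfil these rules, only the correct data will be used in the derivation". The divisor then becomes the count of days actually available. This text stands under interim analyses. SAP 3.2, however, says that diary compliance (Baseline and Weeks 2, 4, 8, 12 and 16) is calculated on the days that enter the frequency and severity analysis, and allows fewer than seven of them under 4.3.2.

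SAP 4.6.1, the final co-primary analysis, does not repeat the rule. It refers to 4.2.11, which divides by 7. Week 1 uses the first seven available post-baseline days, with no provision for fewer.

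**The concern.** Membership of the primary efficacy set depends on how many diary days a subject completes after randomisation. Early departure may be related to dose: Protocol 5.1.3 lists headache, diarrhoea and somnolence as possibly related to NT-814, and Protocol 9.4.1 provides for intolerable treatment-related events. Exclusions could then differ by arm, and the comparison would no longer be between the groups as randomised and dosed.

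The stated justification is that the endpoint needs seven days. If the SAP's derivation does not need them, the exclusion discards usable data for no analytical reason. The MMRM in SAP 4.6.1 accepts subjects with incomplete visits, so the model does not need the condition either.

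**Working it through.** **1. Plan's own figure.** Inputs from SAP 4.1: difference 8 − 4 = 4, SD 4.4, two-sided alpha 0.05, power 95%. Normal approximation: n = 2 × (1.960 + 1.645)² × 4.4² / 4² = 31.4, so 32. The exact t calculation gives 33 per group (power 95.3%), as stated. This point does not change that figure; 33 is used below only as an arm size.

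**2. The rules side by side.**

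| Rule | Fewest diary days | Where the days must fall |
|---|---|---|
| FAS entry (SAP 3.1, Protocol 11.3) | 7 | anywhere after treatment start |
| Visit value (SAP 4.3.2, via 3.2) | 1 | within 14 days before the visit, at least one in the last 7 |
| Visit value (SAP 4.6.1 referring to 4.2.11) | 7, divisor 7 | before the visit |
| Week 1 value (SAP 4.6.1) | 7, no short-data rule | first available post-baseline days |

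**3. Not necessary.** Take a subject with five diary days, all in Days 1 to 14 and the latest on Day 10, who attends Week 2 on Day 15 and then leaves. She has 5 < 7 days and is outside the FAS. Under 4.3.2 all five days lie in the 14-day window and Day 10 lies in the last seven (15 − 7 = Day 8 onwards). Her Week 2 value is the sum divided by 5, and Week 2 is a visit in the MMRM.

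**4. Not sufficient.** Take a subject with diary days on Days 1 to 7 only. She enters the FAS. The Week 4 window for a visit on Day 29 opens on Day 15 (29 − 14), and the Week 12 window for a visit on Day 85 opens on Day 71 (85 − 14). She has no value at either co-primary visit.

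**5. No later analysis restores the excluded.** The modified FAS and the Per Protocol set (SAP 3.1) are both subsets of the FAS, and SAP 4.6 runs efficacy on these sets only.

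**6. Size.** The documents give no count of subjects with fewer than seven diary days. As an illustration, assume *e* of 33 are excluded from one active arm and none from placebo, those kept average a reduction of 8 against 4 on placebo, and those excluded have a true reduction *r* between 0 and 4. The difference with everyone included is [8(33 − e) + r·e]/33 − 4:

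- e = 1: 3.88 (r = 4) to 3.76 (r = 0), against 4.00 analysed.
- e = 3: 3.64 (r = 4) to 3.27 (r = 0), against 4.00 analysed.

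These differences assume that the excluded subjects' true outcomes are known at the analysis visit. They are not what a wider FAS would recover, because most such subjects have no Week 4 or Week 12 value and would inform those estimates only through Week 1 or Week 2.

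**7. The divisor.** Three diary days at an assumed 10 flushes per day give 30/3 = 10.0 with the actual number of days, but 30/7 = 4.3 under a literal reading of 4.2.11. Admitting short diaries without settling this would create a false improvement of 10.0 − 4.3 = 5.7 per day.

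**The case against.** The protocol is consistent within itself: it defines the endpoint on seven days and asks for seven. The short-data rule is per visit and written for the interim analyses, while the final-analysis section points to a formula that divides by 7. The rules can also coexist. A subject with three days before Week 12 and at least four elsewhere is in the FAS and gets a Week 12 value. All this stands, and it places the conflict in the SAP, where the cross-reference in 3.2 brings the 4.3.2 rule into the analysis. It does not remove the conflict.

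The excluded subjects would add little. They are mostly very early leavers, and the MMRM uses data only up to treatment discontinuation. Analysis sets are fixed before unblinding, and SAP 4.4 already tabulates reasons for exclusion. This also stands: it limits the size and makes exclusions visible, but restores nobody.

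Two stronger readings are tempting. A reader might infer that everyone who stops drug in the first week is removed. The criterion is diary days, not dosing, and Protocol 7.4 asks for continued follow-up, so a subject who stops drug but completes seven diary days stays in.

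A reader might also infer inflated responder rates. If two of 33 were excluded and 60% of the other 31 responded, counting the two as failures would give 18.6/33 = 56%. That needs a non-responder rule, which the plan lacks. SAP 4.2.1 bases percentages on non-missing values and 4.2.7 makes no substitutions, so a subject without a Week 4 or Week 12 value would stay out of the denominator under any FAS definition.

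**Conclusion.** The point holds as a minor improvement. The 7-day condition is neither necessary nor sufficient for a co-primary value under the SAP's own derivation, it selects on post-randomisation behaviour, and no planned efficacy set undoes the selection. This rests on reading SAP 3.2 as applying the 4.3.2 rule to the final analysis visits. If 4.6.1 and 4.2.11 are read alone, the SAP has no short-data rule for those visits, and the text still needs reconciling.

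The size cannot be computed from the documents and is probably small. The illustrated 3.27 to 3.88 against 4.00 should not be read as the bias in the planned MMRM: the arm-specific exclusions and the outcomes of those excluded are assumptions.

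**What to change.** - **SAP 3.1 and Protocol 11.3:** define the FAS as randomised, dosed subjects with a baseline and at least one derivable post-baseline hot flush value. Delete the 7-day condition and the parenthesis that calls it a requirement. This still conditions on some post-randomisation data, but a subject with no derivable value contributes nothing to the MMRM in any case.
- **SAP 4.6.1:** state the rule for fewer than seven days once, with the actual number of days as denominator, and extend it to Week 1.
- **SAP 4.2.11:** replace the fixed divisor of 7 accordingly, so that short diaries do not give falsely low frequencies.
- **SAP 4.4:** show FAS exclusions and reasons by arm.
- **SAP section 5:** record the change; it now reports none.

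The cost is a few sentences, settled before unblinding, and no new data. The downside is that a few early-visit values rest on fewer days and are noisier.
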